8.1 Definitions

Unanticipated Problems Involving Risk to Subjects or Others

Any incident, experience, or outcome that meets all of the following criteria:

- Unexpected in nature, severity, or frequency (i.e. not described in study-related documents such as the IRB-approved protocol or consent form, the investigators brochure, etc)
- Related or possibly related to participation in the research (i.e. possibly related means there is a reasonable possibility that the incident experience, or outcome may have been caused by the procedures involved in the research,
- Serious (as defined below) "Serious" is different than "severe" as reported in the CTC criteria that applies a grade to the AE.

Adverse Event

An *adverse event* (AE) is any symptom, sign, illness or experience that develops or worsens in severity during the course of the study. Intercurrent illnesses or injuries will be regarded as adverse events. Abnormal results of diagnostic procedures are considered to be adverse events if the abnormality:

- results in study withdrawal
- is associated with a serious adverse event
- is associated with clinical signs or symptoms
- leads to additional treatment or to further diagnostic tests
- is considered by the investigator to be of clinical significance

Serious Adverse Event

Adverse events are classified as serious or non-serious. A *serious adverse event* is any AE that is:

- fatal
- life-threatening
- requires or prolongs hospital stay
- results in persistent or significant disability or incapacity
- a congenital anomaly or birth defect
- an important medical event

Important medical events are those that may not be immediately life threatening, but are clearly of major clinical significance. They may jeopardize the subject, and may require intervention to prevent one of the other serious outcomes noted above. For example, drug overdose or abuse, a seizure that did not result in in-patient hospitalization, or intensive treatment of bronchospasm in an emergency department would typically be considered serious.

All adverse events that do not meet any of the criteria for serious should be regarded as **non**serious adverse events.

Based on previous clinical trials of sulforaphane in humans [43, 48, 51], we do not anticipate any significant adverse events with Avmacol[®], though the following gastrointestinal symptoms may potentially occur with greater frequency:

- Nausea and vomiting
- Abdominal pain
- Large or soft stools

- The abnormality is of a degree that requires active management; e.g. change of dose, discontinuation of the drug, more frequent follow-up assessments, further diagnostic investigation, etc.

Hospitalization, Prolonged Hospitalization or Surgery

Any adverse event that results in hospitalization or prolonged hospitalization will be documented and reported as a serious adverse event. Any condition responsible for surgery will be documented as an adverse event if the condition meets the criteria for an adverse event.

Neither the condition, hospitalization, prolonged hospitalization, nor surgery are reported as an adverse event in the following circumstances:

• Hospitalization or prolonged hospitalization for diagnostic or elective surgical procedures for a preexisting condition. Surgery should *not* be reported as an outcome of an adverse event if the purpose of the surgery was elective or diagnostic and the outcome was uneventful.

8.2 Recording of Adverse Events

At each contact with the subject, the investigator will seek information on adverse events by specific questioning and, as appropriate, by examination. Information on all adverse events will be recorded immediately in the source document, and also in the appropriate adverse event log of the case report form (CRF). All clearly related signs, symptoms, and abnormal diagnostic procedures results will be recorded in the source document, though grouped under one diagnosis.

All adverse events occurring during the study period will be recorded in the adverse event log. The clinical course of each event will be followed until resolution, stabilization, or until it has been determined that the study treatment or participation is not the cause. Serious adverse events that are still ongoing at the end of the study period will be followed up, either by phone call or clinic visit, to determine the final outcome. Any serious adverse event that occurs after the study period and is considered to be possibly related to the study treatment or study participation will be recorded and reported immediately to the FDA, UNC Biomedical IRB, and DSMB.

8.3 Reporting of Serious Adverse Events and Unanticipated Problems

The study PI will immediately report any serious adverse events to the FDA, UNC Biomedical IRB, and DSMB meeting the following 3 criteria:

- related to study participation,
- unexpected, and
- serious or involve risks to subjects or others (see definitions, section 8.1).

If the report is supplied as a narrative, the minimum necessary information to be provided at the time of the initial report includes:

- Study identifier
- Study Center
- Subject number
- A description of the event
- Date of onset

- Current status
- Whether study treatment was discontinued
- The reason why the event is classified as serious
- Investigator assessment of the association between the event and study treatment

8.3.1 Investigator reporting: notifying the study sponsor

The proposed trial is investigator-initiated, and thus the investigator is also the sponsor. Any study-related unanticipated problem posing risk of harm to subjects or others, and any type of serious adverse event, will be reported to the FDA within 7 calendar days using FDA Form 3500A for mandatory reporting. SAEs meeting the criteria outlined in the beginning of section 8.3 will also be reporting to the UNC Biomedical IRB by the study PI via IRBIS (the IRB information system for UNC) within 7 calendar days of becoming aware of the adverse event. Significant new information on ongoing serious adverse events will be provided promptly to the FDA and UNC IRB. A written report of the SAE will also be provided to the DSMB for committee review within 14 calendar days of the event.

8.3.2 Investigator reporting:

For reportable deaths, the initial submission to the UNC IRB will be made by contacting the IRB Director or Associate Director. The AE/Unanticipated Problem Form is required as a follow up to the initial submission.

Other Reportable events:

For clinical drug trials, the following events are also reportable to the UNC IRB:

- Any adverse experience that, even without detailed analysis, represents a serious unexpected adverse event that is rare in the absence of drug exposure (such as agranulocytosis, hepatic necrosis, Stevens-Johnson syndrome).
- Any adverse event that would cause the sponsor to modify the investigator's brochure, protocol or informed consent form, or would prompt other action by the IRB to assure protection of human subjects.
- Information that indicates a change to the risks or potential benefits of the research, in terms of severity or frequency. For example:
 - Safety monitoring indicates that a particular side effect is more severe, or more frequent than initially expected.
 - A paper is published from another study that shows that an arm of your research study is of no therapeutic value.
 - Change in FDA safety labeling or withdrawal from marketing of a drug, device, or biologic used in a research protocol.
 - Breach of confidentiality
 - Change to the protocol taken without prior IRB review to eliminate apparent immediate hazard to a research participant.
 - Incarceration of a participant when the research was not previously approved under Subpart C and the investigator believes it is in the best interest of the subject to remain on the study.
 - Complaint of a participant when the complaint indicates unexpected risks or the complaint cannot be resolved by the research team.
 - Protocol violation (meaning an accidental or unintentional deviation from the IRB approved protocol) that in the opinion of the investigator placed one or more participants at increased risk, or affects the rights or welfare of subjects. If a large number of protocol deviations are identified, or if they are deemed to affect patient safety or the overall efficacy of the trial, the protocol deviations will also be reported to the DSMB.

8.3.3 Investigator reporting:

Not applicable, as this is a single-site study.

8.3.4 Sponsor reporting: Notifying the FDA

The study PI (study sponsor) will promptly complete a written IND safety report for any adverse event meeting the following criteria:

• Within 7 calendar days

Any study event that is:

- associated with the use of the study drug
- unexpected,
- fatal or life-threatening, and
- Within 15 calendar days
Any study event that is:

- associated with the use of the study drug,
- unexpected, and
- serious, but not fatal or life-threatening
 or-
- a previous adverse event that was not initially deemed reportable but is later found to fit the criteria for reporting (reporting within 15 calendar days from when event was deemed reportable).

Additional reporting requirements

The study PI (sponsor) will identify in IND safety reports all previous reports concerning similar adverse events and analyze the significance of the current event in light of the previous reports.

Reporting Process

Adverse events will be submitted on FDA Form 3500A or in a narrative format, along with FDA form 1571. If supplied as in a narrative format, the minimum information to be supplied is noted above at the beginning of section 8.3.

8.4 Unblinding Procedures

The study team will make every effort to maintain blinding of treatment assignment for both subject and investigator for the entire duration of the individual subject's study participation. Treatment unblinding will be limited to the occurrence of a serious adverse event (SAE) that the independent medical monitor determines is possibly related to study treatment and study participation. In the event of such an unanticipated problem, study staff will contact UNC IDS via the on-call [contact]) to report the occurrence of the event and request that treatment assignment status be disclosed to the independent medical monitor. The study staff and participant and caregiver will remain blinded to treatment. The treatment status will be faxed by IDS to the medical monitor and relevant medical personnel involved in treating the subject (e.g., emergency room physician, primary care physician). A narrative description of the SAE and treatment status will be documented in the CRF, and the FDA and UNC IRB will be promptly notified as specified above in Section 8.3.1.

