The week 4 visit will take approximately 1 hour. The subject and his caregiver will return to the clinic for a follow-up visit that will include measurement of vital signs (height, weight, blood pressure, heart rate, and temperature), caregiver completion of behavioral outcome measures (SRS-2, RBSR, and ABC), and clinician-rated CGI-Severity and CGI-Improvement scores. The adverse event log will also be completed by the study physician. Caregivers will be asked to report any changes in concurrent medications or non-pharmacological treatments since the previous study visit. The medication log and returned tablets will be reviewed/ counted for treatment compliance, and the next 5-week supply of investigational drug will be dispensed to the participant and his caregiver. Caregivers will be instructed to administer any unused tablets from the previous bottle before starting the new supply.

6.6 Week 8 Follow-Up Visit:

The week 8 visit will take approximately 1 hr. to complete. The patient and his caregiver will return to the clinic for a follow-up visit that will include measurement of vital signs (height, weight, blood pressure, heart rate, and temperature), caregiver completion of behavioral outcome measures (SRS-2, RBSR, and ABC), and clinician-rated CGI-Severity and CGI-Improvement scores.

The adverse event log will also be completed by the study physician. Caregivers will be asked to report any changes in concurrent medications or non-pharmacological treatments since the previous study visit. The medication log and returned tablets will be reviewed/ counted for treatment compliance, and the next 5-week supply of investigational drug will be dispensed to the participant and his caregiver. Caregivers will be instructed to administer any unused tablets from the previous bottle before starting the new supply. Participants will be given a new OMNIGene-Gut stabilization kit for collection of a stool sample at home in the 48 hr prior to the scheduled Week 12 visit. The research team will remind the participant and his caregiver of how to collect the sample and instruct to return it at the next visit.

6.7 Week 12 Follow-Up Visit:

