8.5 Stopping Rules

• If a participant experiences significant adverse events that affect tolerability, may reasonably be related to taking the investigational product, and do not meet the protocol definition for a serious AE (including non-extreme behavioral changes), the dose may be reduced by approximately 30% according to the following dose modification schedule:

Weight category	Prescribed weight- based dose of glucoraphanin	Prescribed # of tablets	70% of weight-based dose (ie, 30% reduction)	Prescribed # tablets for reduced dose (rounded to nearest 15 mg increment)*
<100 lb	45 mg	3	31.5 mg	2
100-125 lb	75 mg	5	52.5 mg	3
126-175 lb	90 mg	6	63 mg	4
176-199 lb	105 mg	7	73.5 mg	5
≥ 200 lb	120 mg	8	84 mg	6

*Rounded down if equidistant between two 15 mg dosing increments

- If the dose is reduced during the course of the study, the participant will continue the lowered dose for the remainder of the study. If adverse events do not improve within 14 days of lowering the dose, the investigational product may be permanently discontinued at the discretion of the treating study physician, participant, and participant's guardian. If a participant exhibits extreme exacerbation of behavioral symptoms (such as self-injurious behavior or aggression) that do not improve substantially following a dose reduction and are determined "probably" or "definitely" related to taking the investigational product, the investigational product may be permanently discontinued sooner than 14 days post-reduction, and the DSMB will be notified. As individuals with ASD often have cyclical changes in behavior independent of medication effects, the study staff will rely on caregivers' experience with the participant to determine if any observed behavior changes are within the expected range for that individual. If the investigational product is stopped permanently, the participant and his caregiver will be asked to complete the remainder of the study visits, return any unused study drug, and repeat safety lab studies.
- If a participant has a seizure while taking the study medication, the study medication will be stopped, and the DSMB will be notified. The participant will be evaluated by the study PI and the participant's primary care physician, treated, and monitored appropriately for the duration of the study. The participant and his caregiver will be asked to return to complete the remainder of the study visits, return any unused study drug, and repeat safety lab studies.

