9.3 Case Report Forms

The study case report form (CRF) is the primary data collection instrument for the study. All data requested on the CRF must be recorded. All missing data must be explained. If a space on the CRF is left blank because the procedure was not done or the question was not asked, write "N/D". If the item is not applicable to the individual case, write "N/A". All entries should be printed legibly in black ink. If any entry error has been made, to correct such an error, draw a single straight line through the incorrect entry and enter the correct data above it. All such changes must be initialed and dated. DO NOT ERASE OR WHITE OUT ERRORS. For clarification of illegible or uncertain entries, print the clarification above the item, then initial and date it.

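### Section 8.4 keeps study staff blinded after an SAE code break, yet sends the treatment arm into the CRF they work from, with no limit on access or timing

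*Combined protocol and SAP*

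**What the plan says.** Section 8.4 limits unblinding to an SAE that the independent medical monitor considers possibly related. Study staff ask IDS to disclose the assignment, but not to themselves: "The treatment status will be faxed by IDS to the medical monitor and relevant medical personnel involved in treating the subject". On everyone else the section is explicit: "The study staff and participant and caregiver will remain blinded to treatment". It then adds: "A narrative description of the SAE and treatment status will be documented in the CRF".

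Section 5.8 sets the general rule that the study team and subjects stay blinded until data collection has ended. Section 9.3 says what the CRF is: "The study case report form (CRF) is the primary data collection instrument for the study". Section 8.2 makes the adverse event log part of the CRF, and of that log the visit descriptions in sections 6.5 to 6.8 say: "The adverse event log will also be completed by the study physician".

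**The concern.** The paragraph protects the blind in one sentence and puts the arm into the study team's own record shortly afterwards. If the CRF entry is made in the usual way, by the people who normally complete the CRF and at the time of the event, they learn the assignment of a participant who is still being assessed. At stake are the ratings made by clinicians after that moment: CGI-S, CGI-I, the CGI component of responder and partial-responder status, and the assessment of further adverse events. These are the measurements that blinding of the study team is meant to protect.

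**Working it through.** No stated figure in the plan bears on this point, so the check is a comparison of sections, followed by a count of what could be exposed.

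1. **What the treatment status is.** In section 8.4 it is what IDS faxes in answer to a request for the assignment. It therefore means the arm, not whether the participant is on or off drug.
2. **Who is meant not to know it.** Study staff, participant and caregiver (8.4), and the study team until data collection ends (5.8).
3. **Who works in the CRF.** It is the main data collection instrument (9.3), and the study physician completes its adverse event log (8.2; 6.5 to 6.8).
4. **Whether a barrier exists.** Sections 5.8, 8.4, 8.6, 9.2 and 9.3 and the monitoring plan in Appendix 6B describe no sealed page, late entry or entry by the monitor alone. The access limits that do exist (9.2 for source documents, Appendix 6B for paper charts and electronic files) admit study staff. They keep outsiders out and do not separate blinded from unblinded staff.
5. **Whether ratings follow.** Under 8.5, a participant whose drug is stopped for a related SAE is asked to complete the remaining visits. Under 4.4.1, a subject leaves the study itself only if consent is revoked.
6. **Who rates.** The study physician is named as CGI-S rater at screening and baseline (6.2, 6.3). At Weeks 4 to 16 the CGI is described only as rated by clinicians (6.5 to 6.8). That this is the study physician is an inference: no other rater is named.

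**Count of exposed ratings.** Post-baseline CGI visits are Weeks 4, 8, 12 and 16. The CGI-I proportion endpoint uses Weeks 12 and 16 only, whereas section 7.2 models CGI-S longitudinally.

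| Code break falls | CGI visits still to come | Of these, used for the CGI-I proportion |
|---|---|---|
| before Week 4 | 4 | 2 |
| Weeks 4 to 8 | 3 | 2 |
| Weeks 8 to 12 | 2 | 2 |
| Weeks 12 to 16 | 1 | 1 |

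**Weight of one participant.** With 27 per arm (7.1), 1/27 = 3.7 percentage points and 2/27 = 7.4 points. This is the most that one or two participants can move an arm's proportion, and only if knowing the arm shifts a CGI-I score across the boundary between 2 and 3.

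**How many participants.** The plan gives no expected SAE rate. The earlier autism trial reported no SAEs but two seizures in 45 subjects, and section 8.1 would typically class even a non-hospitalised seizure as serious. Taking that rate at face value gives 54 × 2/45 = 2.4 events over both arms. This is only a rough guide. Both subjects had a seizure history, this trial excludes seizures in the previous 12 months, and a code break also needs the monitor to judge the event possibly related.

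**The case against.** The best defence is that section 8.4 does not say who enters the status or when. Entry by the medical monitor, or after the participant's last visit, would satisfy both sentences, and the explicit blinding rules in 8.4 and 5.8 favour reading it that way. This stands to the extent that the two instructions are not logically impossible to follow together. It does not remove the problem, because the text provides for neither arrangement and the default use of a CRF is the opposite.

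A second defence also stands: the monitor judges relatedness before the code is released, so that judgement on the triggering SAE is not contaminated. Only later assessments are at risk.

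Several stronger readings are tempting and are not supported:

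- **The regulatory reports also unblind the investigator.** Section 8.3.1 notes that "the investigator is also the sponsor", so a reader might infer that filing the SAE report reveals the arm. The minimum report content in section 8.3 does not include the arm, and 8.3.1 does not ask for it.
- **The primary care physician passes the code on.** On a seizure, section 8.5 says: "The participant will be evaluated by the study PI and the participant's primary care physician". A reader might infer that the code travels by that route. The primary care physician is only an example of a possible recipient in 8.4, and nothing says that the two evaluate jointly or share the assignment.
- **The bias runs one way.** A code break can occur in either arm, and knowing the arm could raise or lower a rating. The documents give no direction.
- **The primary result is compromised.** The SRS-2 is completed by the caregiver, who is to stay blinded. Responder status also requires a 10-point fall on that scale, so CGI-I alone cannot confer it.

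**Conclusion.** The point holds as a conflict in the unblinding procedure. Section 8.4 requires the arm to be recorded in the study team's working instrument without any restriction on access or timing, and ordinary compliance would break the blinding stated in 8.4 itself and in 5.8. The consequence is confined to the few participants with a possibly related SAE and to ratings after the code break: CGI-S, CGI-I, the CGI part of responder status, and later adverse event assessments. The primary SRS-2 endpoint is not directly exposed. The ceiling of 3.7 percentage points per participant on an arm's CGI-I proportion is not an estimate of bias, and no direction is established. The conclusion assumes that CRF entries are made by study staff at about the time of the event; its reach to the CGI assumes that the study physician is the rater at Weeks 4 to 16. The correction is worth making because it costs little.

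**What to change.** Amend section 8.4 so that:

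- the CRF holds only the SAE narrative, the date of the code release and the recipients;
- IDS and the medical monitor keep the treatment status in a restricted file at least until that participant's Week 16 assessments are complete;
- any report that does need the arm receives it directly from IDS or the monitor;
- clinicians who are given the code are asked not to pass it to the study team.

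The release time needs reconciling in the same edit. Section 5.8 keeps the team blinded until all data collection has ended, while section 6.8 has study staff obtain the assignment from IDS and share it at the Week 16 visit.

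The cost is a few sentences and a minor procedure for IDS and the monitor. Disclosure to the monitor and treating clinicians is unchanged, and no dose, stopping or other clinical rule is touched.
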